**NOTES:**

- Additional parameters may be included as required.
- Lambda\_z is the terminal phase rate constant.
- The 10 PK parameters AUC(0-t), AUC(0-24), AUC(0-inf), AUCex, Cmax, tmax, t1/2, CL, Vdss and Vc will be derived from phoenix and sent to S&P. The radiometric IV and oral dose will be calculated by Covance and sent to S&P. Additional parameters will be derived by S&P including CLr, ML(iv), ML(po), Fg, EH, Fabs, F and the treatment ratios

**Table 2** **Derived Urine and Faeces Pharmacokinetic Parameters**

Parameter	Parameter Description
Ae[urine]	Total radioactivity recovered in the urine (Ae[urine]) calculated for each collection interval per subject and treatment period as:  Ae[urine]=(concentration in urine sample x collected sample weight) for each urine collection interval, eg 0-6, 6-24, 24-48, etc.
Cumulative Ae[urine]	Cumulative total radioactivity recovered in the urine (Cumulative Ae[urine]) calculated for each cumulative collection interval per subject and treatment period as:  Cumulative Ae[urine]= summation of Ae[urine] for each urine collection within the cumulative urine collection interval, eg 0-24, 0-48, etc.
Fe%[urine]	% of total dose excreted as total radioactivity (Fe%[urine]) for each collection interval per subject and treatment period, will be estimated as:  Fe%[urine]=(Ae[urine]) for each collection period)/Dose*100.  Where the dose is the radiolabelled [  C]-GSK2269557, that is in period 1 radiometric iv dose, in period 2 radiometric oral dose
Cumulative Fe%[urine]	Cumulative % of total dose excreted as total radioactivity (Cumulative Fe%[urine]) for each cumulative collection interval per subject and treatment period, will be estimated as:  Cumulative Fe%[urine]=summation of Fe%[urine] for each urine collection within the cumulative urine collection interval, eg 0-24, 0-48, etc.

Parameter	Parameter Description
Ae[faeces]	
Total radioactivity recovered in the faeces (Ae[faeces]) calculated for each collection interval per subject and treatment period as
 $Ae[\text{faeces}] = (\text{concentration in faecal homogenate aliquot analysed} \times \text{weight of homogenate aliquot analysed}) \times (\text{total homogenate weight} / \text{collected sample weight})$ 
for each faecal collection interval, eg 0-24, 24-48, etc

Cumulative Ae[faeces]	
Cumulative total radioactivity recovered in the faeces (Cumulative Ae[faeces]) calculated for each cumulative collection interval per subject and treatment period as
 $\text{Cumulative Ae}[\text{faeces}] = \text{summation of Ae}[\text{faeces}]$ 
for each faecal collection within the cumulative faecal collection interval, eg 0-24, 0-48, etc

Fe%[faeces]	
% of total dose excreted as total radioactivity (Fe%[faeces]) for each collection interval per subject and treatment period will be estimated as:
 $Fe\%[\text{faeces}] = (Ae[\text{faeces}] \text{ for each collection period}) / \text{Dose} * 100.$ 
Where the dose is the radiolabelled [C]-GSK2269557, that is in period 1 radiometric iv dose, in period 2 radiometric oral dose

Cumulative Fe%[faeces]	
Cumulative % of total dose excreted as total radioactivity (Cumulative Fe%[faeces]) for each cumulative collection interval per subject and treatment period will be estimated as:
 $\text{Cumulative Fe\%}[\text{faeces}] = \text{summation of Fe\%}[\text{faeces}]$ 
for each faecal collection within the cumulative faecal collection interval, eg 0-24, 0-48, etc.

Ae[total]	
Total radioactivity recovered in total excretion (sum of urine and faecal excretion), Ae[total] will be estimates by collection interval for each subject and treatment period as:
 $Ae[\text{total}] = Ae[\text{urine}] + Ae[\text{faeces}]$
Cumulative Ae[total]	
Total radioactivity recovered in total excretion (sum of urine and faecal excretion), cumulative Ae[total] will be estimates by cumulative collection interval per subject and treatment period as:
 $\text{Cumulative Ae}[\text{total}] = \text{summation of Ae}[\text{total}]$ 
for each total excretion collection within the cumulative total excretion collection interval, eg 0-24, 0-48, etc

Fe%[total]	
% of total dose excreted as total radioactivity (Fe%[total]) for each collection period will be estimated for each subject and treatment period as:
 $Fe\%[\text{total}] = Fe\%[\text{urine}] + Fe\%[\text{faeces}]$
Cumulative Fe%[total]	
Cumulative % of total dose excreted as total radioactivity (Cumulative Fe%[total]) for each cumulative collection period will be estimated for each subject and treatment period as:
 $\text{Cumulative Fe\%}[\text{total}] = \text{Cumulative Fe\%}[\text{urine}] + \text{Cumulative Fe\%}[\text{faeces}]$ 
for each total excretion collection within the cumulative total excretion collection interval, eg 0-24, 0-48, etc

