10.3.1. Pharmacokinetic Analyses

Plasma GSK2269557 concentration-time data will be listed for each participant and summarised by treatment and planned sampling time. [¹⁴C]-GSK2269557 and radioactivity concentrations in plasma will be reported similarly. Individual participant, mean, and median plasma GSK2269557, [¹⁴C]-GSK2269557 and total radioactivity concentration-time profiles will be plotted for each treatment on both a linear and semi-log scale.

Pharmacokinetic analysis will be performed by or under the direct auspices of Clinical Pharmacology Modelling & Simulation, GSK. Plasma GSK2269557, [¹⁴C]-GSK2269557 and total radioactivity concentration-time data will be analysed by non-compartmental methods with WinNonlin Version 6.3 or above. Calculations will be based on the actual sampling times recorded during the study. From the plasma concentration-time data the following pharmacokinetic parameters will be determined, for GSK2269557, [¹⁴C]-GSK2269557 and total radioactivity, as data permits: maximum observed plasma concentration (Cmax), time to Cmax (tmax), area under the plasma concentration-time curve [AUC(0-t) and AUC(0-inf)], terminal phase rate constant (λ_z), and apparent terminal phase half-life ($t_{1/2}$) following inhaled, oral and IV dosing. Additionally, volume and clearance will be derived following IV dosing. These parameters will be summarised descriptively.

Absolute bioavailability will be estimated for the inhaled and oral doses for each participant and will be summarised.

Derivation of the urine and faecal radioactivity parameters will be the responsibility of the IVIVT department within GSK. The following parameters will be determined from the urine and faecal radiolabelled drug-related material (radioactivity) data, and will be listed and summarised by treatment:

- Absolute amount excreted and percentage excreted in urine (Ae[urine] and Fe%[urine]) within each collection period and cumulative urinary recovery and fraction excreted over the total collection period.
- Absolute amount excreted and percentage excreted in faeces (Ae[faecal] and Fe%[faecal]) with each collection period and cumulative faecal recovery and fraction excreted over the total collection period and cumulatively over the collection period.
- Total excretion (sum of urine and faecal excretion), Ae [total] and Fe% [total] will be calculated by collection interval for each participant.

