## 8. PHARMACOKINETIC ANALYSES

The plasma pharmacokinetic concentrations will have different nomenclatures dependent on the method of measuring. For measured concentrations of GSK2269557 in blood plasma, the nomenclature [C]-GSK2269557 describes the parent GSK2269557 concentration derived via analysis by liquid chromatography (LC) + Accelerator Mass Spectrometry (AMS), whereas GSK2269557 describes the parent GSK2269557 concentration derived via liquid chromatography-tandem mass spectrometry (LC/MS). It is expected that, for period 1, the radiolabelled iv dose will be measured using LC+AMS and will be labelled “[C]-GSK2269557”, the non-radiolabelled inhaled dose will be measured using LC/MS and will be labelled “GSK2269557”. For period 2, the radiolabelled oral dose will be measured using LC/MS and will be labelled “GSK2269557”. For each period the total radioactivity will be measured by AMS and will be labelled “Total Radioactivity”. However, these methods may be adapted if necessary.

The reconciliation of the PK Case Report Form (CRF) and SMS2000 data will be performed by, or under the direct auspices of, Clinical Pharmacology Science and Study Operations (CPSSO), GlaxoSmithKline.

Derivation of plasma pharmacokinetic parameters for [C]-GSK2269557, total radioactivity and GSK2269557 will be performed by, or under the direct auspices of, Clinical Pharmacology Modelling and Simulation (CPMS), GlaxoSmithKline.

Derivation of urine/faeces total radioactivity parameters will be performed by, or under the direct auspices of Bioanalysis, Immunogenicity and Biomarkers (BIB), PTS IVIVT, GlaxoSmithKline.

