### **8.2.2. Summary Measure**

A primary objective is to determine total radioactivity (drug related material) in plasma following a single IV microtracer of [14C]-GSK2269557 (concomitant with an inhaled non-radiolabelled GSK2269557 dose) and a single oral dose of [14C]-GSK2269557. To assess this, the plasma PK parameters: AUC (0-inf), AUC (0-t), AUC (0-24), %AUCex, Cmax, tmax, t1/2 of total drug-related material (radioactivity) will be summarised and listed.

The additional primary objective is to determine the rate and extent of excretion of total radioactivity in urine and faeces and the total recovery of radioactivity following a single IV microtracer of [14C]-GSK2269557 (concomitant with an inhaled non-radiolabelled dose) and a single oral dose of [14C]-GSK2269557. To assess this, the PK parameters: Ae and Fe% will be summarised and listed for urine faeces and total (Urine + Faeces).

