### 11.4.3. Reporting Standards for Pharmacokinetic

Pharmacokinetic Concentration Data	
PC Windows Non-Linear (WNL) File	PC WNL file (CSV format) for the non compartmental analysis by Clinical Pharmacology Modelling and Simulation function will be created according to PKOne. Note: Concentration values will be imputed as per GUI_51487
Descriptive Summary Statistics, Graphical Displays and Listings	Refer to IDSL PK Display Standards. Refer to IDSL Statistical Principle 6.06.1. Note: Concentration values will be imputed as per GUI_51487 for descriptive summary statistics/analysis and summarized graphical displays only.
Pharmacokinetic Parameter Derivation	
Plasma PK Parameter to be Derived by Programmer	The following PK parameters will be derived by the Programmer: CL r , ML(iv), ML(po), F g , E H , F abs , F(Oral, (0-t)), F(Oral, (0-∞)), F(inhaled, (0-t)), F (inhaled, (0-∞)) and the Parent GSK2269557/ Total Radioactivity ratio for Cmax, AUC(0-t), AUC(0-24) and AUC(0-∞). note: Parent GSK2269557/ Total Radioactivity ratios will be either GSK2269557/ Total Radioactivity or [14C]-GSK2269557/ Total Radioactivity depending on the method of sample analyses and are of interest for the radiolabelled IV and oral dose.
Urine and Faeces PK Parameter to be Derived by Programmer	The following PK parameters will be derived by the Programmer: cumulative Ae, Fe% and cumulative Fe%.
Pharmacokinetic Parameter Data	
Is NQ impacted PK Parameters Rule Being Followed	No.
Descriptive Summary Statistics, Graphical Displays and Listings	Refer to IDSL PK Display Standards. Refer to PKOne

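### The printed SAP formula for radioactivity recovered in faeces does not scale the aliquot up to the whole homogenate; if executed, it understates faecal recovery by collected weight / aliquot weight

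*SAP*

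**What the plan says.** SAP Section 8.1.2, Table 2, defines Ae[faeces] for each collection interval as a product of two brackets. The first is the "concentration in faecal homogenate aliquot analysed" multiplied by the weight of that aliquot. The second is the ratio "total homogenate weight} / \text{collected sample weight" (the brace and backslash code is left over from typesetting).

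The urine row of the same table is simpler: "concentration in urine sample x collected sample weight". There, the collected sample weight is the weight of the whole collection. The faecal row does not define the term.

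The rest of Table 2 builds on interval Ae[faeces]. It is divided by the radiometric dose to give Fe%[faeces], added to the urine amount to give Ae[total] and Fe%[total], and summed over intervals for the cumulative forms.

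On responsibility, SAP Section 8 says: "Derivation of urine/faeces total radioactivity parameters will be performed by, or under the direct auspices of Bioanalysis, Immunogenicity and Biomarkers". Protocol Section 10.3.1 likewise assigns the derivation to the sponsor's IVIVT department. SAP Section 11.4.3 has the programmer derive only cumulative Ae, Fe% and cumulative Fe%; interval Ae is not on that list.

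**The concern.** The first bracket is the radioactivity in the aliquot alone. To reach the whole collection it must be multiplied by total homogenate weight over aliquot weight. The printed second bracket is total homogenate weight over collected weight, which is only the dilution ratio of the homogenate. The units balance either way, so a dimensional check would not reveal the problem.

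Cumulative urinary and faecal excretion as a percentage of dose is a primary endpoint, and total recovery is part of the same primary objective (Protocol Section 4; SAP Sections 2.2 and 8.2.2). SAP Tables 2.17 to 2.20 and Figures 2.10 to 2.17 all carry the faecal and total amounts. Neither document gives another formula for interval Ae[faeces], so a programmer or quality checker has no correct version to compare with the values received.

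**Working it through.** **Inputs.** The documents print no weights and no recovery figure, so there is no stated number to reproduce. Notation:

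- C: radioactivity per gram of homogenate, measured in the aliquot (SAP Table 2)
- Wa: weight of aliquot analysed (SAP Table 2)
- Wh: total homogenate weight (SAP Table 2)
- Wc: collected sample weight (SAP Table 2), read as the weight of faeces collected

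Three things support that reading of Wc. The urine row uses the same term for the whole collection. Protocol Section 9.5.3 has the weight of faeces collected in each interval recorded in the CRF. And the faecal formula already has a separate term for the aliquot weight.

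**Algebra.**

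- True amount = C × Wh
- Printed formula = (C × Wa) × (Wh / Wc) = true amount × Wa / Wc
- True / printed = Wc / Wa

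Wh cancels, so the degree of dilution does not matter.

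**Numerical check (assumed values).** C = 1000 per g, Wa = 0.5 g, Wc = 150 g, Wh = 450 g.

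- True: 1000 × 450 = 450,000
- Printed: 1000 × 0.5 × 450 / 150 = 1,500
- Ratio: 450,000 / 1,500 = 300 = 150 / 0.5
- With the divisor changed to Wa: 1000 × 0.5 × 450 / 0.5 = 450,000
- With the first weight changed to Wc instead: 1000 × 150 × 450 / 150 = 450,000

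Either one-term substitution restores the true amount.

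**Range (assumed weights).** With Wc from 50 to 300 g and Wa from 0.2 to 5 g, the factor runs from 50 / 5 = 10 to 300 / 0.2 = 1500. A true interval Fe%[faeces] of 50 would print as 50 / 10 = 5.0% at one end and 50 / 1500 = 0.03% at the other. At the factor of 300 it would print as 0.17%.

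**Effect on total recovery.** The urine term is correct, so the printed total is urine + faeces / k, where k = Wc / Wa. The splits below are assumed, each with a true total of 90% of dose.

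| True urine / faeces (% of dose) | Printed total, k = 30 | Printed total, k = 300 |
|---|---|---|
| 5 / 85 | 5 + 85/30 = 7.8 | 5 + 85/300 = 5.3 |
| 20 / 70 | 20 + 70/30 = 22.3 | 20 + 70/300 = 20.2 |
| 70 / 20 | 70 + 20/30 = 70.7 | 70 + 20/300 = 70.1 |

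At k = 300 the totals are low by factors of 90/5.3 = 17, 90/20.2 = 4.4 and 90/70.1 = 1.3.

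**Other readings.**

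- If the divisor meant the portion taken from the homogenate, Wc would equal Wa, the formula would reduce to C × Wh, and there would be no error (factor 1).
- If the concentration were per gram of original faeces, the formula would still fail, by Wc² / (Wa × Wh) = 150² / (0.5 × 450) = 100. The text says homogenate, so this reading does not fit.

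**The case against.** The strongest reply is that the printed formula may never be executed. The bioanalysis group supplies interval Ae, so the Table 2 row may only describe an input calculated under that group's own procedure. Protocol Sections 9.5.3 and 9.5.5 leave faecal processing and sample analysis details to the Study Reference Manual, which is not available here. Discharge in Period 2 also depends on percentage of dose measured in faecal homogenates (Protocol Section 5.1.2), so some working calculation must exist before the SAP outputs are produced. This stands: the documents do not show that reported results will be wrong. Nor do they show a correct calculation anywhere.

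A second reply is that this is a wording slip on an undefined term, and that one reading gives no error. A slip is plausible. The no-error reading is the less natural one, because it gives the aliquot weight two names in one formula and departs from the urine row.

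A third reply is that the error would be noticed and could be reversed. With mainly faecal excretion, a total of 5 to 8% would be implausible, and the recorded weights and archived raw data would probably allow recalculation. With mainly urinary excretion, a total near 70% could pass as incomplete collection, although faecal recovery near zero should still raise a question. The Protocol Synopsis says the elimination routes are not fully elucidated in humans, so no firm expected split exists against which to judge the result.

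Finally, every numerical factor above rests on assumed weights and splits. That is right, and only the ratio Wc / Wa is exact.

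**Conclusion.** The concern holds. As printed, and with the divisor read as the weight of faeces collected, the formula returns the true faecal amount times aliquot weight over collected weight. It therefore understates faecal recovery whenever the aliquot weighs less than the collection. That is certain as algebra. The size is illustrative: 10- to 1500-fold for faecal recovery under the assumed weights, and less for total recovery, depending on the urine/faeces split.

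The consequence is conditional on the bioanalysis group following the printed formula. Even so, this is the only formula for interval Ae[faeces] in either document, it governs a primary excretion endpoint, and on its natural reading it gives a wrong value. It should be corrected before the analysis. Urinary recovery, and the other primary objective on plasma total radioactivity, are not affected.

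**What to change.** In SAP Table 2, state Ae[faeces] as the concentration in the homogenate (per gram of homogenate) multiplied by total homogenate weight, summed over the homogenates in the interval. Equivalently, keep the present form and replace the divisor with the weight of homogenate aliquot analysed. Define each weight term in the table. Ask the bioanalysis group to confirm in writing that its interval Ae calculation matches.

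The cost is one formula, a few definitions and one confirmation. The corrected form uses only quantities already named in the printed formula, so no new data are needed.

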**NOTES:**

- Additional parameters may be included as required.

## **8.2. Primary Pharmacokinetic Analyses**

### **8.2.1. Endpoint / Variables**

#### **8.2.1.1. Drug Concentration Measures**

Refer to [Appendix 4](#): Data Display Standards & Handling Conventions (Section 11.4.3 Reporting Standards for Pharmacokinetic)

#### **8.2.1.2. Derived Pharmacokinetic Parameters**

Pharmacokinetic parameters will be calculated as described in Section [8.1.2](#).

### **8.2.2. Summary Measure**

A primary objective is to determine total radioactivity (drug related material) in plasma following a single IV microtracer of [14C]-GSK2269557 (concomitant with an inhaled non-radiolabelled GSK2269557 dose) and a single oral dose of [14C]-GSK2269557. To assess this, the plasma PK parameters: AUC (0-inf), AUC (0-t), AUC (0-24), %AUCex, Cmax, tmax, t1/2 of total drug-related material (radioactivity) will be summarised and listed.

The additional primary objective is to determine the rate and extent of excretion of total radioactivity in urine and faeces and the total recovery of radioactivity following a single IV microtracer of [14C]-GSK2269557 (concomitant with an inhaled non-radiolabelled dose) and a single oral dose of [14C]-GSK2269557. To assess this, the PK parameters: Ae and Fe% will be summarised and listed for urine faeces and total (Urine + Faeces).

